6.3 Measures to Minimize Bias: Randomization and Blinding

An interactive response technology (IRT) will be used for assigning eligible study participants to a treatment regimen (as applicable) based on a predetermined production randomization and/or packaging schedule provided by UCB (or designee). The randomization schedule will be produced by the IRT vendor. The IRT will generate individual assignments for kits of study medication, as appropriate, according to the visit schedule.

To enroll a study participant (Visit 1), the Investigator or designee will contact the IRT and provide brief details about the participant to be enrolled. Each study participant will receive a 5-digit number assigned at Screening that serves as the study participant identifier throughout the study. The study participant number will be required in all communication between the Investigator or designee and the IRT regarding a particular study participant. Study participant numbers and kit numbers will be tracked via the IRT.

To randomize a study participant, the Investigator or designee will contact the IRT and provide brief details about the study participant to be randomized. The IRT will automatically inform the Investigator or designee of the study participant's randomization number. The IRT will allocate

kit numbers to the study participant based on the participant number during the course of the study. The randomization number must be incorporated into the eCRF.

The randomization will be stratified by the following:

- MG-specific autoantibody (MuSK+ or AChR+)

6.3.1 Procedures for maintaining and breaking the treatment blind

6.3.1.1 Maintenance of study treatment blind

All study participant treatment details, rozanolixizumab treatment arm, planned dose, or placebo will be allocated and maintained by the IRT system.

The following individuals will receive the randomization code at the start of the study:

- Designated bioanalytical staff analyzing PK samples
- IRT provider

Study site pharmacists or other suitably qualified site personnel who are responsible for preparation of IMP treatments will have access to treatment allocations for individual study participants via the IRT. The unblinded pharmacy monitors from the Contract Research Organization (CRO), and the Clinical Supply Manager will also have access to the treatment allocations and to the drug accountability records, if applicable.

The following individuals may, as necessary, have access to the randomization code as indicated:

- Sponsor Patient Safety staff as needed for reporting SAEs to regulatory authorities.
- Members of the IDMC who participate in unblinded sessions will be given information about the IMP allocation for those study participants for whom data are provided at these sessions.
- CRO staff supporting preparation of the data outputs for the IDMC review and/or any interim analyses.
- Independent Medical Monitor external to the sponsor for monitoring unblinded clinical laboratory data, such as total IgG levels.

If IgG levels drop below 1g/L, the IMP must be temporarily discontinued. If IgG levels is ≥ 1 and < 2 g/L, and study participant is experiencing a nonserious infection which is persisting or recurrent, rozanolixizumab treatment may be temporarily discontinued (Section 7.1.4).

Temporary treatment discontinuation due to low IgG levels may informally unblind the treatment assignment to the participant and site personnel. Therefore, infusions will be continued but given as mock infusions with only placebo irrespective of IMP designation. Allocation of mock kit numbers will be handled via the IRT. An unblinded Medical Monitor will inform the Investigator of the initiation of mock infusions and bring attention to any potential infection risk. The Medical Monitor will continue to review available safety information for these study participants (eg, AEs for infection and white cell count) while the IgG levels are at the protocol-defined low threshold values, and directly contact the Investigator should this review identify additional information that may be important in the care of the study participants. When the IgG levels have returned to the protocol-defined levels to re-initiate IMP (Section 7.1.4), the unblinded Medical Monitor will inform the Investigator of this decision. Based on the clinical situation, the Investigator has the option of holding the dose until deemed appropriate.

Further details are provided in the study manual and site blinding plan.

6.3.1.2 Breaking the treatment blind in an emergency situation

In the event of an emergency, it will be possible to determine to which treatment arm and dose the study participant has been allocated by contacting the IRT. All sites will be provided with details of how to contact the system for code breaking at the start of the study. The Medical Monitor or equivalent should be consulted prior to unblinding, whenever possible.

The Clinical Project Manager and Medical Monitor will be informed immediately via the IRT when a code is broken, but will remain blinded to specific treatment information. Any unblinding of the study medication performed by the Investigator must be recorded in the source documents and on the Study Termination eCRF page.

Inadvertent unblinding has to be listed as a major protocol deviation.

6.4 Treatment Compliance

Drug accountability must be recorded on the Drug Accountability form (see Section 6.2.1).

6.5 Concomitant Medication(s)/Treatment(s)

6.5.1 Permitted concomitant treatments (medications and therapies)

All concomitant treatments permitted during the study are presented in Table 6-1.

Any violation of the permitted treatment criteria would lead to prohibited treatment and should be discussed with the Investigator, sponsor and Medical Monitor.

Table 6-1: Permitted Concomitant Treatments

Permitted Medications	Dose	Comment
Oral Corticosteroids (eg, prednisolone)	No specific requirements	Stable for █████ prior to Baseline ^a
Methotrexate	≤30mg/week	Treated for previous █████ and on stable dose for █████ prior to Baseline ^a
Mycophenolate mofetil	≤3g/day	Treated for previous █████ and on stable dose for █████ prior to Baseline ^a
Cyclosporine ^b	≤5mg/kg/day for unmodified ≤4mg/kg/day for modified (microemulsion)	Treated for previous █████ and on stable dose for █████ prior to Baseline ^a
Azathioprine	≤3mg/kg/day	Treated for previous █████ and on stable dose for █████ prior to Baseline ^a
Cholinesterase inhibitors	≤600mg Pyridostigmine/day	Stable dose not required – dose █████ of efficacy outcomes

Permitted Medications	Dose	Comment
Tacrolimus ^c	≤5mg/day	Treated for previous [REDACTED] and on stable dose for [REDACTED] prior to Baseline ^a

^a Must also be stable for duration of study.

^b Doses higher than listed are permissible if trough level is ≤300ng/mL.

^c If the total daily weight-based dose is >5mg, then a plasma trough level should be checked to ensure study participant is not above the recommended therapeutic range.

The use of medicinal cannabidiols and medicinal marijuana (prescribed by a physician) is also permitted. When applicable, the study participant must be on a stable dose of cannabidiols and/or medicinal marijuana for [REDACTED] prior to Screening, and remain stable for the duration of the study.

6.5.2 Prohibited concomitant treatments (medications and therapies)

The following concomitant medications are prohibited during the study:

- All biologics including rituximab
- Cyclophosphamide
- Pimecrolimus
- IPP-201101 (Lupuzor™)
- Immunoabsorption
- Vinca alkaloids (vincristine, vinblastine)

If a study participant needs or takes any prohibited medication or therapy, the Investigator will (where possible) discuss with the Medical Monitor and/or sponsor's Study Physician and a decision will be made whether the study participant can continue in the study or must be withdrawn. If the study participant is treated with rituximab, the study participant must be withdrawn from the IMP, but should be encouraged to continue with Observation Period visits.

For study participants who require a medical or surgical procedure that requires the use of general anesthesia, discussion must occur prior to the procedure with the Medical Monitor or study physician. In an emergency situation, discussion should occur as soon as possible after the procedure, such that a decision on the study participant's continued participation in the study can be made.

6.5.3 Treatments specific to NMJ interference

Treatments could interfere with the function of the NMJ (and which therefore could impair study participants with MG), such as, but not limited to, include the following medications:

- botulinum toxin
- aminoglycoside antibiotics
- tetracycline antibiotics
- penicillamine

- magnesium

For a more detailed list please refer to the MGFA medication list (<https://myasthenia.org/What-is-MG/MG-Management/Cautionary-Drugs>). The benefit-risk of starting these medications should be carefully considered by the Investigator, and where possible, the Investigator will discuss with the Medical Monitor and/or sponsor's Study Physician prior to initiating therapy that can affect the NMJ.

6.5.4 Rescue therapy

Rescue therapy for the study will consist of IVIg or PEX. The study site will supply rescue therapy that will be obtained locally.

Study participants who experience disease worsening (eg, an increase of 2 points on the MG-ADL or 3 points on the QMG scale between two consecutive visits) may be considered for rescue therapy at the discretion of the Investigator.

Study participants who need rescue therapy during the Treatment Period may receive IVIg or PEX at the discretion of the Investigator, will complete any subsequent visit(s) and will move into the Observation Period.

For study participants receiving IVIg or PEX as rescue therapy, the date and time of administration as well as the name and dosage regimen of the rescue therapy must be recorded.

6.6 Dose Modification

There is no dose modification allowed in this study.

6.7 Treatment after the End of the Study

Study participants who need rescue therapy during the 8-week Observation Period, or complete the Observation Period without rescue therapy, will be invited to enroll into the OLE study. They will be randomized to one of two rozanolixizumab dose arms, equivalent to approximately [REDACTED] or [REDACTED]. Alternatively, if a study participant opts to receive IVIg or PEX during the Observation Period, he or she will complete the Observation Period and will not be eligible to enter the OLE study.

In the case of prolonged hypogammaglobulinemia after treatment discontinuation, study participants must be followed up until IgG levels return to values within the normal range or to individual Baseline values.

For study participants not enrolling into the OLE study, there are no plans for continued provision with rozanolixizumab after the end of the study. The participant should discuss any needed care after the study with their healthcare provider.

7 DISCONTINUATION OF STUDY MEDICATION AND PARTICIPANT DISCONTINUATION/WITHDRAWAL

[figure not shown]
7.1 Discontinuation of Study Medication

7.1.1 Liver Chemistry Stopping Criteria

Discontinuation of study treatment for abnormal liver function should be considered by the Investigator when a study participant meets one of the conditions outlined in [Figure 7-1](#) and [Figure 7-2](#), or if the Investigator believes that it is in the best interest of the study participant.

[figure not shown]
The study participant should follow the visit schedule as described in the protocol and the eCRF be completed accordingly.

Figure 7-1: Liver Chemistry Stopping Criteria and Increased Monitoring Algorithm

ALT=alanine transaminase; AST=aspartate aminotransferase; INR=international normalized ratio; SAE=serious adverse event; ULN=upper limit of normal

Figure 7-2: Liver Chemistry Increased Monitoring Algorithm with Continued Study Intervention for Participants with ALT $\geq 3xULN$ but $\leq 8xULN$

ALT=alanine transaminase; AST=aspartate aminotransferase; bili=bilirubin; INR=international normalized ratio; SAE=serious adverse event; ULN=upper limit of normal

Specific assessments and follow-up actions for potential drug-induced liver injury are provided in Appendix 6 (Section 10.6).

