7.1.3 Discontinuation due to other adverse events or medical conditions

Study participants **must** permanently discontinue rozanolixizumab **and** move into the Observation Period if any of the following events occur:

1. Study participant develops an illness that would interfere with his/her continued exposure to rozanolixizumab.
2. Study participant has new onset or recurrent neoplastic disease (except for superficial basal or squamous cell carcinoma of the skin not requiring targeted biological therapy, chemotherapy or radiation).
3. Study participant has a serious infective episode requiring hospitalization or iv antibiotic therapy (ie, bacteremia or sepsis, meningitis, osteomyelitis or septic arthritis, pneumonia, or visceral abscess) (see Section 10.25).
4. Study participant has an AE of severe or serious infusion or anaphylactic reaction requiring corticosteroid and/or epinephrine therapy (see Section 10.28) (Sampson et al, 2006).
5. Study participant experiences a serious or recurrent (ie, second occurrence) severe AE of headache, which is considered related to the study medication in the opinion of the investigator.
6. Study participant has a TB test that is confirmed positive or any further evidence suggestive of potential TB infection (eg, exposure) and further examinations result in a diagnosis of active TB or LTBI (Section 8.2.6).
7. Study participant meets potential drug-induced liver injury permanent discontinuation criteria.

If a NTMBI is identified during a study, the same withdrawal procedures as those used for an active TB infection identified during the study should be followed.

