
NOTES :
 
^a Details of liver chemistry stopping criteria and required actions and follow-up assessments after liver stopping or monitoring event are given in Section 10.6 and Appendix 6. All events of ALT $\geq 3xULN$ and bilirubin $\geq 2xULN$ (>35% direct bilirubin) or ALT $\geq 3xULN$ and international normalized ratio (INR) >1.5, if INR measured, may indicate severe liver injury (possible Hy's Law) and must be reported as an SAE (excluding studies of hepatic impairment or cirrhosis).
 
^b Local urine testing will be standard for the protocol unless serum testing is required by local regulation or IRB/IEC.
	

Investigators must document their review of each laboratory safety report.

Laboratory/analyte results that could unblind the study will not be reported to investigative sites or other blinded personnel until the study has been unblinded.

10.3 Appendix 3: Adverse Events – Definitions and Procedures for Recording, Evaluating, Follow-up, and Reporting

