10.6 Appendix 6: Liver Safety – Suggested Actions and Follow-up Assessments

Participants with potential drug-induced liver injury must be assessed to determine if study medication must be discontinued. In addition, all concomitant medications and herbal supplements that are not medically necessary should also be discontinued.

Investigators should attempt to obtain information on study participants in the case of study medication discontinuation to complete the final evaluation.

Study participants with potential drug-induced liver injury should not be withdrawn from the study until investigation and monitoring are complete. All results of these evaluations and observations, as well as the reason(s) for study medication discontinuation and/or participant withdrawal (if applicable), must be recorded in the source documents. The CRF must document the primary reason for discontinuation of study medication.

A specific monitoring plan must be agreed between the UCB study physician and the Investigator for study participants who have ALT >5 ULN. The monitoring plan should include any necessary follow-up assessments (until resolution of the abnormal lab values).

Table 10–2: Liver Chemistry Stopping Criteria and Follow-Up assessments

Liver Chemistry Stopping Criteria	
ALT-absolute	ALT ≥8xULN
ALT Increase	ALT ≥5xULN but <8xULN persists for ≥2 weeks ALT ≥3xULN but <5xULN persists for ≥4 weeks
Bilirubin^{a, b}	ALT ≥3xULN and bilirubin ≥2xULN (>35% direct bilirubin)
INR²	ALT ≥3xULN and international normalized ratio (INR) >1.5, if INR measured
Cannot Monitor	ALT ≥5xULN but <8xULN and cannot be monitored weekly for ≥2 weeks ALT ≥3xULN but <5xULN and cannot be monitored weekly for ≥4 weeks
Symptomatic^c	ALT ≥3xULN associated with symptoms (new or worsening) believed to be related to liver injury or hypersensitivity
Suggested Actions and Follow up Assessments	
Actions	Follow Up Assessments

 • Immediately discontinue study medication. • Report the event to UCB within 24 hours. • Complete the liver event case report form (CRF), and complete a serious adverse event (SAE) data collection tool if the event also met the criteria for an SAE.^b 	
 • Viral hepatitis serology^d • Obtain INR and recheck with each liver chemistry assessment until the transaminases values show downward trend • Only in those with underlying chronic hepatitis B at study entry (identified by positive hepatitis B surface antigen,

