
 • Perform liver chemistry follow-up assessments. • Monitor the participant until liver chemistry test abnormalities resolve, stabilize, or return to Baseline (see MONITORING). • Do not restart/rechallenge participant with study medication. • If restart/rechallenge not allowed per protocol or not granted, permanently discontinue study medication and continue participant in the study for any protocol specified follow-up assessments. Consider the need for a toxicology Screening. 
MONITORING:
 
For bilirubin or INR criteria
 
 • Repeat liver chemistry tests (include ALT, aspartate transaminase [AST], alkaline phosphatase, bilirubin) and perform liver event follow-up assessments within 24 hours. • Monitor participant twice weekly until liver chemistry test abnormalities resolve, stabilize, or return to Baseline. • A specialist or hepatology consultation is recommended. 
For all other criteria
 
 • Repeat liver chemistry tests (include ALT, AST, alkaline phosphatase, bilirubin) and perform liver chemistry follow-up assessments within 24 to 72 hours. • Monitor participants weekly until liver chemistry abnormalities resolve, stabilize, or return to Baseline. 	
quantitative hepatitis B deoxyribonucleic acid (DNA) and hepatitis delta antibody^e)
 
 • Obtain blood sample for pharmacokinetic (PK) analysis as soon as feasible after the most recent dose^f • Serum creatine phosphokinase and lactate dehydrogenase (LDH) • Fractionate bilirubin, if total bilirubin $\geq 2xULN$ • Obtain complete blood count with differential to assess eosinophilia • Record the appearance or worsening of clinical symptoms of liver injury, or hypersensitivity, on the adverse event (AE) report form • Record use of concomitant medications (including acetaminophen, herbal remedies, and other over-the-counter medications) on the concomitant medications CRF. • Record alcohol use on the liver event alcohol intake CRF • Exclude pregnancy • Urine drug screen 
For bilirubin or INR criteria:
 
 • Anti-nuclear antibody, anti-smooth muscle antibody, Type 1 anti-liver kidney microsomal antibodies, and quantitative total IgG or gamma globulins. • A serum acetaminophen adduct assay for assessing the potential acetaminophen contribution to liver injury in participants with definite or likely acetaminophen use in the preceding week. • Liver imaging (ultrasound, magnetic resonance, or computerized tomography) and/or liver biopsy to evaluate liver disease; complete Liver Imaging and/or Liver Biopsy CRFs.

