---	---

- a. Serum bilirubin fractionation should be performed if testing is available. If serum bilirubin fractionation is not immediately available, discontinue study medication if ALT $\geq 3xULN$ **and** bilirubin $\geq 2xULN$. Additionally, if serum bilirubin fractionation testing is unavailable, **record the absence/presence of detectable urinary bilirubin on dipstick** which is indicative of direct bilirubin elevations suggesting liver injury.
- b. All events of ALT $\geq 3xULN$ **and** bilirubin $\geq 2xULN$ (>35% direct bilirubin) or ALT $\geq 3xULN$ **and** INR >1.5 may indicate severe liver injury (**possible ‘Hy’s Law’**) **and must be reported as an SAE (excluding studies of hepatic impairment or cirrhosis)**. The INR measurement is not required and the stated threshold value will not apply to participants receiving anticoagulants.
- c. New or worsening symptoms believed to be related to liver injury (such as fatigue, nausea, vomiting, right upper quadrant pain or tenderness, or jaundice) or hypersensitivity (such as fever, rash or eosinophilia).
- d. Includes: Hepatitis A immunoglobulin M (IgM) antibody; HBsAg and HBcAb; hepatitis C RNA; cytomegalovirus IgM antibody; Epstein-Barr viral capsid antigen IgM antibody (or if unavailable, heterophile antibody or monospot testing); and hepatitis E IgM antibody.
- e. If hepatitis delta antibody assay cannot be performed, it can be replaced with a polymerase chain reaction (PCR) of hepatitis D RNA virus (where needed) [Le Gal et al, 2005]. Record the date/time of the PK blood sample draw and the date/time of the last dose of study medication prior to the PK blood sample draw on the CRF. If the date or time of the last dose is unclear, provide the participant’s best approximation. If the date/time of the last dose cannot be approximated OR a PK sample cannot be collected in the time period indicated above, do not obtain a PK sample. Instructions for sample handling and shipping are in the IMP Handling Manual.

Table 10–3: Liver chemistry increased monitoring criteria with continued study medication

Liver Chemistry Increased Monitoring Criteria	
Criteria	Actions

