
ALT $\geq 5xULN$ and $< 8xULN$ and bilirubin $< 2xULN$ without symptoms believed to be related to liver injury or hypersensitivity, and who can be monitored weekly for 2 weeks.
 
OR
 
ALT $\geq 3xULN$ and $< 5xULN$ and bilirubin $< 2xULN$ without symptoms believed to be related to liver injury or hypersensitivity, and who can be monitored weekly for 4 weeks.
	
 • Notify the Sponsor Medical Monitor within 24 hours of learning of the abnormality to discuss participant safety. • Participant can continue study medication. • Participant must return weekly for repeat liver chemistry tests (ALT, AST, alkaline phosphatase, bilirubin) until the abnormalities resolve, stabilize, or return to baseline. • If at any time, the participant meets liver chemistry stopping criteria, proceed as described in Section 7.1.1. • If ALT decreases from ALT $\geq 5xULN$ and $< 8xULN$ to $\geq 3xULN$ and $< 5xULN$, continue to monitor liver chemistries weekly. • If, after 4 weeks of monitoring, ALT $< 3xULN$ and bilirubin $< 2xULN$, monitor participants twice monthly until liver chemistry tests resolve, stabilize, or return to baseline.

ALT=alanine aminotransferase; AST=aspartate aminotransferase; ULN=upper limit of normal

10.7 Appendix 7: Medical Device Incidents – Definition and Procedures for Recording, Evaluating, Follow-up, and reporting

Not applicable.

This document cannot be used to support any marketing authorization application and any extensions or variations thereof.

PUBLIC COPY

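### The protocol gives the liver stop inconsistent force: Section 7.1.1 words it as something to consider, Table 10-2 and Section 7.1.3 as mandatory, and the Figure 7-2 title misplaces ALT of exactly 8xULN

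*Protocol*

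**What the plan says.** Four places in the protocol treat the liver stop as mandatory:

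- Appendix 6, Table 10-2, lists the stopping criteria. Its actions include "Immediately discontinue study medication" and "Do not restart/rechallenge participant with study medication".
- Footnote a to that table covers the case where bilirubin cannot be fractionated at once: "If serum bilirubin fractionation is not immediately available, discontinue study medication if ALT" is ≥3xULN with bilirubin ≥2xULN.
- Section 7.1.3 says participants must permanently stop if any listed event occurs. Item 7 of that list is "Study participant meets potential drug-induced liver injury permanent discontinuation criteria".
- Appendix 2, note a: "Details of liver chemistry stopping criteria and required actions and follow-up assessments after liver stopping or monitoring event are given in Section 10.6".

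Two places are softer:

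- Section 7.1.1, whose title is Liver Chemistry Stopping Criteria: "Discontinuation of study treatment for abnormal liver function should be considered by the Investigator". The trigger is a condition in Figure 7-1 or 7-2, or the Investigator's view of the participant's best interest.
- The title of Appendix 6 describes its content as "Suggested Actions and Follow-up Assessments", and Table 10-2 heads its action rows in nearly the same words.

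Table 10-3, the increased-monitoring table, links the two sets: "If at any time, the participant meets liver chemistry stopping criteria, proceed as described in Section 7.1.1".

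On the threshold, Table 10-2 stops at ALT ≥8xULN and Table 10-3 continues treatment only for ALT <8xULN. The Figure 7-2 title, in Section 7.1.1 and in the list of figures, sets the continued-treatment band at ALT ≥3xULN up to and including 8xULN.

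**The concern.** A stopping rule should have the same force wherever a site reads it. Here the section that carries the rule's name, and to which Table 10-3 refers, uses the weakest verb in the protocol for this event. Doses are weekly, so the decision has to be made within days. An Investigator who relies on 7.1.1 could reasonably think that the stop is a matter of judgement and give another dose while further results are awaited. What is at stake is patient safety in a few participants. The Figure 7-2 title adds a small separate error: at one ALT value it says the opposite of the table that it should illustrate.

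**Working it through.** **Is it the same event?** Table 10-3 uses the term liver chemistry stopping criteria and sends the reader to 7.1.1. Table 10-2 uses that term as its title. In the visible text Table 10-2 is the only list of such criteria, so the event that 7.1.1 says to consider and the event for which Table 10-2 orders an immediate stop are the same.

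**Which force is intended?** Three things point to mandatory. Table 10-2 and its footnote a use unconditional imperatives. Section 7.1.3 uses *must*. Appendix 2 calls the actions required. Two smaller points agree. Section 7.1.2 says that a participant who meets the QTc criteria will discontinue, so the protocol uses directive wording for a comparable stop. The summary of changes for the current amendment lists item 7 of 7.1.3 as new, which makes the mandatory stop the sponsor's latest position. Against this stand the label Suggested in Appendix 6 and its opening sentence, which has participants assessed to decide whether the drug must be stopped. These add to the inconsistency and do not settle it. That the stop is meant to be mandatory is an inference, but a well-supported one.

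**Boundary check at ALT = 8.0xULN**

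- Table 10-2 (≥8xULN): stop.
- Table 10-3 (<8xULN): not in the continue band.
- Figure 7-2 title (≤8xULN): in the continue band.

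The three limits agree at every other value, so the conflict is at that single point.

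**Upper bound on doses at stake.** From the Schedule of Activities (Section 1.3), doses fall on Days 1, 8, 15, 22, 29 and 36, six in all. Scheduled chemistry after Baseline in the Treatment Period falls on Days 8, 22, 36 and 43. Further doses = number of dosing days later than (day first seen + required persistence). Table 10-2 allows 0 once a criterion is met, so each count is also the largest possible difference from a mandatory stop.

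- Criteria that one result can meet (ALT ≥8xULN, or ALT ≥3xULN with bilirubin ≥2xULN, with INR >1.5 if measured, or with symptoms), and the Cannot Monitor rows if met on that result:
  - Day 8 leaves Days 15, 22, 29, 36 = 4.
  - Day 22 leaves Days 29, 36 = 2.
  - Day 36 or 43 leaves 0.
- ALT ≥5 to <8xULN persisting 2 weeks:
  - Day 8 + 14 = Day 22, leaving 2.
  - Day 22 + 14 = Day 36, leaving 0.
- ALT ≥3 to <5xULN persisting 4 weeks:
  - Day 8 + 28 = Day 36, leaving 0.
  - Day 22 + 28 = Day 50, leaving 0.

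These counts assume nominal visit days, a first elevation in a scheduled sample, and a central-laboratory result that arrives after that day's dose and before the next. If the qualifying result is in hand before the dose on the day the criterion is met, counts for criteria met on Days 8 to 36 rise by 1.

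**The case against.** The strongest reply is that a reader sent to 7.1.1 is not left there. The section ends by referring to Appendix 6 for assessments and follow-up actions, and Table 10-2 is in that appendix. Someone reading Table 10-3 has only just passed Table 10-2. Item 7 of 7.1.3, under the same 7.1 heading, already says *must*. All of this stands. A reader might infer from 7.1.1 that the protocol has no mandatory liver stop, or that the Table 10-3 route ends at a discretionary one. The documents support neither reading.

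It is also fair that the sentence in 7.1.1 has a mixed scope. It covers the Figure 7-2 monitoring band and best-interest stops, where discretion is right. The bodies of both figures are not shown and may carry firm stop instructions. If they do, the sentence would still be at odds with its own figures.

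Safeguards limit the harm. Stopping events go to the sponsor within 24 hours. ALT >5xULN needs a monitoring plan agreed with the sponsor's study physician. Participants in the monitoring band are notified to the Medical Monitor within 24 hours and retested weekly. Possible Hy's Law events must be reported as SAEs. None of these gives the person deciding on the next dose one clear instruction.

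The label Suggested is weak evidence by itself, because it also covers the follow-up tests and the bullets beneath it are imperatives. The 8xULN discrepancy is a slip at one value, and the two tables show which rule is meant.

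**Conclusion.** The inconsistency is real and should be corrected. The practical risk is a stop that is delayed or treated as discretionary because instructions conflict; it is not that a mandatory rule is missing. The documents give no rate of liver events, and I assume that few participants would be affected.

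Four further doses of six, after a criterion met on a Day 8 result, is a remote upper bound and not an expectation. To reach it, dosing would have to continue for four weeks against Table 10-2, item 7 and the sponsor notifications.

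A reader might also infer a restart route from the conditional rechallenge bullet in Table 10-2. The outright ban just before it closes that route.

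The correction changes no analysis, and I see no material effect on the primary or formally tested secondary results. The conclusion rests on the visible text of 7.1.1 and the Figure 7-2 title, and on reading Table 10-2 as the criteria meant by item 7.

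**What to change.** - In 7.1.1, state that a participant who meets any Table 10-2 stopping criterion must permanently discontinue study medication. Keep the softer verb only for monitoring-band and best-interest cases.
- In 7.1.3 item 7, cite Table 10-2.
- In the Figure 7-2 title and the list of figures, change the upper limit from ≤8xULN to <8xULN.
- Optional tidying: drop Suggested from the discontinuation action in Table 10-2 and align the Appendix 6 title with Appendix 2.

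The cost is protocol wording. No laboratory threshold in Tables 10-2 or 10-3, visit or analysis changes. When the wording is amended, check the bodies of Figures 7-1 and 7-2 against Table 10-2.
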